## 4 Statistics and Data Analysis

The primary outcome of the study is the success of the products based on assessment of efficacy of the staining dye.

Safety of the dye will be assessed by comparing the surgical outcome of the patients to a similar control group that underwent surgery using the staining dyes presently used in our department (see study endpoints).

Statistical analyses will be performed with R version 3.6.2 or higher. In case of missing values, the underlying missingness process (MCAR, MAR or MNAR) will be investigated and 15 multiple imputations will be performed using the **MICE** R package.

We will test with the statistical test of Jamshidian and Jalal (2010), implemented in the **MissMech** R Package (Jamshidian, Jalal & Jansen, 2014), whether missing data were MCAR. If they were not MCAR, we investigated whether or not the missing mechanism could be explained by baseline characteristics (eg, sociodemographic, medical features) of patients using logistic regression, which would suggest an MAR mechanism. If missing data were not MCAR or MAR, they were considered as MNAR.

For each dataset created, two propensity scores will be performed: a first one between the Monoblue ILM View and the ILM Blue, and a second one between the Monoblue Dual View and Membrane Blue Dual. The next covariates were selected for the propensity score: age, gender, visual acuity of the affected eye, surgery type of the affected eye (vitrectomy only vs phaco and vitrectomy). The Covariate Balancing Propensity Score provided in the R **CBPS** package (Imai & Ratkovic, 2014) will be used to estimate an Average Treatment Effect (ATE). The ATE will be estimated by covariate balancing and requesting an exact match. An absolute standardized difference less than 10–15% will be considered to support the assumption of balance between the groups. Unlike the P-value, this method is not affected by the sample size, and it could be used to compare the relative balance of variables that were measured in different units (Austin, 2011). Results (obtained after matching) will be expressed as the mean and standard deviation (SD) for continuous variables or the percentage for categorical variables. The **survey** R package will be used to perform linear regressions for continuous outcome variables and logistic regressions for binary variable. These regressions

will include the treatment group effect, the weight resulting from the matching, and variables present in the propensity score. This procedure will provide a doubly-robust estimator, which corrected the last remaining possible imbalance between the covariates and produced an unbiased treatment effect (Funk et al., 2010). We will then combine results of the 15 regressions by taking the mean of the estimates of the regression coefficients of the treatment effect and the its associated p-value for each imputed dataset (the so-called, 'Mite approach'), as described by Leyrat et al. (2019). Adjusted P-values less than 0.05 will be considered significant.

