## 2 Study Objectives and Design

### 2.1 Study objectives

To determine efficacy and safety of MONOBLUE DUAL View and MONOBLUE ILM View (study products) vital stains during vitrectomy surgery

Both study products are CE-marked and legally marketed in Europe. The data collection will serve as Post-Marketing Clinical Follow-up according MDR provisions. Retrospective data will also be collected for the two reference products: ILM Blue® (DORC) and Membrane Blue Dual® (DORC) to serve as control. For this purpose, patient data will be used that were collected in studies S61408 (Comparative study 23G vs 27G vitrectomy), S63610 (Comparative study 27G vitrectomy vs larger gauge surgery) and S64913 (EVA Nexus Field Observation Study).

The expected effect of the study products is to provide the retinal surgeon with adequate aid in visualizing the membranes involved in the retinal pathology to treat, thanks to their staining capabilities. The performance of the study products is related to the visualization of retinal tissues (ILM and/or ERM) during the vitrectomy procedure, when these tissues cannot be distinguished accurately enough without staining. Their use allows for better identification of these tissues and facilitates their removal by the surgeon. The clinical benefit of using ophthalmic dyes is to increase the patient's ability to recover anatomically and functionally by allowing more precise surgery with an effective visualization tool.

Along with collecting post-marketing clinical follow-up data on the subject products, the outcomes of the present study results may be used at the UZLeuven Hospital to decide to use Monoblue ILM View and/or Monoblue Dual View as standard-of-care, replacing Membrane Blue Dual and ILM Blue.

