### 2.3 Secondary Endpoints

- Efficacy: subjective assessment of surgical help provided by the product
- Safety:
  - Rate and severity of potential study-related products adverse events
  - Visual outcome at the last postoperative visit

The study hypothesis to be verified is non-inferiority in term of efficacy between study products and comparator based on a binary subjective evaluation of visualization of membranes stained. The proportion of success between study products and comparator will be studied, covariates (age, gender, visual acuity in the affected eye, surgery type being vitrectomy or phaco plus vitrectomy) taken into using a propensity score methodology.

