**Secondary endpoint: assessment of surgical safety**

The following endpoints will be used to determine surgical safety:

- Occurrence of adverse events during or after the surgery, whereby both treatment groups will be compared to the corresponding control groups (see above). Occurrence of adverse events will be collected over the duration of the study and up to week 6-10 postoperative, and will be assessed cumulatively.
- Visual outcome at the last postoperative visit, i.e. week 6-10 after the surgery

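### Safety is compared with controls at p < 0.05 with no interval, acceptable difference or sample-size basis, so a non-significant result cannot support a safety conclusion

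*Combined protocol and SAP*

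**What the plan says.** Section 2.1 sets out to determine both efficacy and safety of the two Monoblue dyes. It adds that the results may be used at the hospital to "decide to use Monoblue ILM View and/or Monoblue Dual View as standard-of-care, replacing Membrane Blue Dual and ILM Blue".

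Section 4 says how safety is judged: "Safety of the dye will be assessed by comparing the surgical outcome of the patients to a similar control group". The subsection on surgical safety in section 5.2 names two endpoints:

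- "Occurrence of adverse events during or after the surgery, whereby both treatment groups will be compared to the corresponding control groups"
- "Visual outcome at the last postoperative visit, i.e. week 6-10 after the surgery"

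The hypothesis in section 2.3 is confined to efficacy: "The study hypothesis to be verified is non-inferiority in term of efficacy between study products and comparator". For inference, section 4 plans to use the survey package "to perform linear regressions for continuous outcome variables and logistic regressions for binary variable", averages the treatment coefficients and p-values over 15 imputed datasets, and closes with "Adjusted P-values less than 0.05 will be considered significant". Neither section gives a confidence interval, an acceptable difference, an expected event rate, a group size or a power figure for safety.

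**The concern.** A test of difference can detect harm but cannot show its absence. For the favourable answer on safety, the plan as written yields only the lack of a significant difference, and fewer eyes make that easier to obtain. The decision named in section 2.1 needs to know how large an excess of harm the data rule out, and the planned output does not contain that quantity. Repairing the efficacy test would not close the gap, because the non-inferiority hypothesis does not extend to safety.

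**Working it through.** There is no figure in the plan to reproduce.

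**Inputs from the plan.** Alpha 0.05 (section 4). Two separate dye pairs (section 4). A window of September 2021 to April 2022 (section 2.4). Controls drawn from three earlier studies (section 2.1).

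**Assumptions, not in the plan.** Two-sided testing, 30 to 100 eyes per group unless stated, a 5% adverse-event risk in controls, and a 0.5 SD visual loss. No loss of effective sample size from weighting is modelled.

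**1. Adverse events, chance of missing a true increase.** Normal approximation to the chi-square test, with p̄ the mean of the two risks:

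power = Φ{[(p1 − p0) − 1.96·√(2p̄(1 − p̄)/n)] / √([p0(1 − p0) + p1(1 − p1)]/n)}

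Example, 5% vs 10% with n = 50 per group: p̄ = 0.075. The null standard error is √(2 × 0.075 × 0.925/50) = 0.0527. The alternative standard error is √((0.0475 + 0.09)/50) = 0.0524. The argument is (0.05 − 1.96 × 0.0527)/0.0524 = −1.02, so power is 15% and the miss rate 85%. Fisher's test, and the chi-square test for 5% vs 15%, were also evaluated by enumerating all possible tables.

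| True risks | Test | 30 per group | 50 per group | 100 per group |
|---|---|---|---|---|
| 5% vs 10% | chi-square, approximate | 89% missed | 85% | 73% |
| 5% vs 10% | Fisher | 98% | 94% | 81% |
| 5% vs 15% | chi-square, enumerated | 74% | 61% | 32% |
| 5% vs 15% | Fisher | 91% | 76% | 41% |

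A larger control group helps only partly. With 50 treated and 150 control eyes, 5% vs 10% is detected in 28% of studies (Fisher 22%), so missed in 72% (78%).

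**2. What a non-significant result leaves open.** If both groups show an observed rate of 5%, the upper 95% limit for the excess is 1.96·√(2 × 0.05 × 0.95/n). This is 11.0 points at n = 30, 8.5 at 50, 6.0 at 100 and 4.3 at 200. If a dye shows no event at all, the exact one-sided 95% upper bound on its rate is 1 − 0.05^(1/n): 9.5% at n = 30, 5.8% at 50 and 3.0% at 100.

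**3. Vision, chance of missing a 0.5 SD loss.** Two-sample t-test with non-centrality 0.5·√(n1·n2/(n1 + n2)).

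| Groups | Non-centrality | Missed, unadjusted |
|---|---|---|
| 20 vs 20 | 1.58 | 66% |
| 30 vs 30 | 1.94 | 52% |
| 30 vs 60 | 2.24 | 40% |
| 50 vs 50 | 2.50 | 30% |
| 64 vs 64 | 2.83 | 20% |

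The planned regressions also contain the propensity-score covariates, among them visual acuity of the affected eye. If that is preoperative acuity and it correlates r with postoperative acuity, the standardised effect becomes 0.5/√(1 − r²): 0.58 at r = 0.5 and 0.70 at r = 0.7. The miss rate falls to 41% and 24% at 30 vs 30, and to 18% and 7% at 50 vs 50, before any loss from weighting. The range of r is an assumption.

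**The case against.** Five points on the other side deserve weight.

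- A reader might infer that a non-significant result will be read as proof of safety. The documents do not say so. They define significance and are silent on what follows from p ≥ 0.05. The gap is a missing rule, not a wrong one. This stands.
- A reader might infer that the p-value is all the safety evidence there will be. It is not. The synopsis and section 2.3 plan the rate and severity of adverse events, and section 4 plans percentages, means with SDs, and pooled effect estimates. This stands: what is missing is the interval and a criterion for reading it.
- A reader might infer that relevant harm would usually be missed on every endpoint. For vision the figures do not support that. A 0.5 SD loss is missed less than half the time from 30 vs 60 upward, and adjustment lowers the chance further. A tripling of adverse events from 5% is missed in fewer than half of studies at 100 per group. This stands.
- The t-test, chi-square and Fisher calculations are not the planned weighted and adjusted regressions, Fisher's test is conservative with few events, and group sizes are unknown, with control groups that could be much larger than assumed. This stands as a limit on precision. It does not rescue the plan for a doubling of a 5% risk, which is missed more often than not at every size in section 1 of the working.
- Safety is a secondary objective, and a formal margin for each safety endpoint is not obligatory. This also stands. Descriptive reporting with intervals would answer the concern.

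**Conclusion.** The point holds in limited form. Section 4 plans a between-group safety comparison whose only inferential criterion is p < 0.05, and nothing in the plan bounds the harm that a non-significant result would leave possible. Such a result cannot support a safety conclusion or the replacement of the current dyes.

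The practical weight is greatest for adverse events: under the assumed sizes of 30 to 100 per group, a doubling from 5% is missed in about 73-89% of studies (chi-square) or 81-98% (Fisher), and a tripling in 61-76% at 50 per group. For vision no general statement is justified, because the chance of missing a loss depends on the group sizes, the SD and the adjustment. All of these figures rest on assumed group sizes and event rates. The absence of an interval and a decision criterion does not.

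**What to change.** In section 4:

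- For each dye pair, report the two-sided 95% confidence interval for the difference in adverse-event risk and in week 6-10 BCVA, from the weighted, adjusted models already planned. Pool over the imputations with a variance that reflects both within- and between-imputation variation, rather than averaging p-values. For the binary endpoint, convert the logistic fit to a risk difference by averaging the predicted risks under each dye.
- For each Monoblue product, report the exact one-sided upper 95% bound of its adverse-event rate.
- State the number of eyes in each of the four dye groups.
- State that p ≥ 0.05 will not be taken as evidence of safety.
- State that safety is reported descriptively with its precision, unless a justified acceptable difference is fixed before data extraction. In that case, conclude that there is no relevant excess harm only if the unfavourable limit lies inside it; otherwise report the result as inconclusive.

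The cost is wording plus interval output; no new patients or data are needed. The drawback is that small groups will often give an inconclusive answer. For illustration only, with margins that are not in the documents: at equal true rates of 5%, one-sided 2.5% and 80% power, n per group = 2 × 0.05 × 0.95 × (1.96 + 0.842)²/m², which is 299 for a 5-point margin and 75 for a 10-point margin.

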**Primary endpoint: Study product efficacy (success, defined as follows):**

From the surgical report, the following data will be extracted:

1. In case of surgery for macular hole or vitreomacular traction:

- A. Was the staining of the ILM satisfactory to initiate the peeling: yes / no
- B. Was the staining of the ILM satisfactory to create the ILM rhexis: yes / no
- C. Was it necessary to use another vital dye in order to obtain satisfactory staining: yes / no

Success is defined as answer “yes” to 1.A and/or 1.B

2. In case of surgery for macular pucker:

- A. Was the staining of the ERM satisfactory for its removal: yes / no
- B. In case the ILM was removed separately from the ERM:
  - i. Was the staining of the ILM satisfactory to initiate the peeling: yes / no
  - ii. Was the staining of the ILM satisfactory to create the ILM rhexis: yes / no
- C. Was MONOBLUE DUAL View repeatedly injected: yes / no
- D. Was it necessary to use another vital dye in order to remove the ERM: yes / no
- E. Was it necessary to use another vital dye in order to remove the ILM: yes / no

Success is defined as “yes” answer to 2.A and 2B.i or 2B.ii

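### The rule that labels missing data MCAR, MAR or MNAR cannot be supported by observed data and changes nothing, and no MNAR sensitivity analysis is planned for staining success

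*Combined protocol and SAP*

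**What the plan says.** Section 4 (Statistics and Data Analysis) sets out three steps. The Jamshidian–Jalal test is used to ask whether data are MCAR. If MCAR is rejected, missingness is related to baseline characteristics of "patients using logistic regression, which would suggest an MAR mechanism". Anything left falls into the third class: "If missing data were not MCAR or MAR, they were considered as MNAR".

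The same section says that, when values are missing, "15 multiple imputations will be performed using the" MICE package. This does not depend on the label. Nor does the pooling: "We will then combine results of the 15 regressions by taking the mean of the estimates of the regression coefficients of the treatment effect". No imputation model for MNAR data is named. Neither Section 4 nor any other section plans a delta-adjusted, tipping-point, best/worst-case or complete-case analysis.

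The analysis supports the claim in Section 2.3: "The study hypothesis to be verified is non-inferiority in term of efficacy between study products and comparator". The outcome is a set of yes/no staining items, collected as Section 5.2 describes: "From the surgical report, the following data will be extracted". For the controls, Section 2.1 says "Retrospective data will also be collected for the two reference products", and names three earlier studies at the centre as the source: two that compare vitrectomy gauges and one field observation study of EVA Nexus.

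**The concern.** The classification promises information that the data cannot give. MAR and MNAR differ only in whether missingness still depends on the unseen value once the observed data are taken into account, and the unseen value is what is not available. A baseline predictor of missingness does not rule out such dependence, and the absence of a predictor does not show it. A report that missing data were found to be MCAR or MAR would therefore reassure without grounds.

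This matters more here than in a prospective trial. The outcome is subjective and is read from surgical reports after the fact. Going by their titles, the control studies were not about dyes. Whether a surgeon noted that staining was satisfactory could depend on how the staining went, and the habit could differ between study-product and control reports. Imputation from observed data cannot correct recording that depends on the answer itself. If the pattern differs between arms, the error goes into the comparison. Under-recorded control successes, or under-recorded study-product failures, would favour non-inferiority. The opposite patterns would work against it. Nothing in the plan would show how far the conclusion depends on this.

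**Working it through.** **No figure to reproduce.** The documents state no sample size, success rate, missing rate or margin. All rates below are assumptions, shown as ranges.

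**Step 1: what the rule can return.** Suppose missingness depends only on the unseen staining result.
- If staining success is unrelated to baseline variables, eyes with and without a recorded answer have the same baseline distribution. The MCAR test then has nothing to detect beyond its false-positive rate, and the usual label is MCAR.
- If success is related to baseline variables, or if missingness also depends on them, a baseline association appears and the label is MAR when it is detected.
- The MNAR label needs MCAR to be rejected and the baseline regression to find nothing. That combination is not evidence that missingness depends on the unseen result.

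**Step 2: bias when successes are under-recorded in one arm.** Let *p* be true success in an arm, and *rs* and *rf* the probabilities that a success and a failure are recorded. If the covariates do not predict success, a MAR analysis returns

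*p·rs* / [*p·rs* + (1−*p*)·*rf*], with missing share 1 − [*p·rs* + (1−*p*)·*rf*].

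With *rf* = 0.9:

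| *p* | *rs* | MAR result | Bias (points) | Missing |
|---|---|---|---|---|
| 0.95 | 0.7 | 0.665/0.710 = 93.7% | −1.3 | 29% |
| 0.90 | 0.7 | 0.630/0.720 = 87.5% | −2.5 | 28% |
| 0.95 | 0.5 | 0.475/0.520 = 91.3% | −3.7 | 48% |
| 0.90 | 0.5 | 0.450/0.540 = 83.3% | −6.7 | 46% |

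A bias of 1.3 to 6.7 points in this direction therefore goes with 28–48% of the arm's outcomes missing.

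**Step 3: the extremes at 5% missing.**
- Every missing eye a success, (*p* − 0.05)/0.95: for *p* = 0.90, 0.85/0.95 = 89.5% (−0.5 points); for *p* = 0.95, 0.90/0.95 = 94.7% (−0.3 points).
- Every missing eye a failure, *p*/0.95: for *p* = 0.90, 0.90/0.95 = 94.7% (+4.7 points); for *p* = 0.95, 0.95/0.95 = 100% (+5.0 points). These mean that half of the arm's failures (0.05/0.10) and all of them (0.05/0.05), respectively, went unrecorded.

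**Step 4: a milder version of the second direction.** With *p* = 0.90, 5% of successes missing and 20% of failures missing, the result is 0.855/(0.855 + 0.080) = 91.4%, a bias of +1.4 points with 6.5% missing (0.90 × 0.05 + 0.10 × 0.20).

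**Step 5: what a sensitivity analysis would show.** With 90% success among recorded eyes and a fraction *f* missing, the bounds are 0.90(1−*f*) and 0.90(1−*f*) + *f*: 85.5–90.5% at 5% missing, 81–91% at 10%, and 72–92% at 20%. The width equals the missing fraction.

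A bias confined to one arm passes in full into the difference between arms.

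**The case against.** The strongest reply is that the labels drive nothing. Section 4 only investigates the mechanism, and its wording on MAR is cautious. The 15 imputations run regardless, so a wrong label cannot move the primary estimate. The main analysis recommended here is essentially the one planned. This stands, and it narrows the point to an uninformative classification and an absent sensitivity analysis.

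A reader might infer that data declared MNAR will routinely be analysed under the assumption just rejected. The text would allow that, but the MCAR test comes first and, as Step 1 shows, the MNAR label should seldom arise. The likelier failing is outcome-dependent missingness that passes as MCAR or MAR. That the imputation is under MAR is itself an inference from MICE with no MNAR option named.

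A reader might also infer that the comparison is in fact biased, perhaps towards the study products. The documents do not support this. Nothing says that the control reports omit staining answers selectively, and either direction is possible. The primary items are intraoperative, so loss to follow-up is not the main route. Section 5.1 makes the investigator responsible for complete forms. That duty helps, but a form filled from a surgical report cannot hold an answer the report lacks. If the items were never recorded for a control group, neither imputation nor a shift would recover them; that would be a different problem.

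Finally, the source cited for pooling concerns partially observed covariates, so outcome imputation may not be the main intention. Section 4 speaks of missing values in general. If eyes without a recorded outcome were simply dropped, the formula in Step 2 would apply equally.

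**Conclusion.** The point holds in limited form. The MAR/MNAR split cannot be made from observed data, no later step uses it, and the non-inferiority comparison of staining success has no planned check against outcome-dependent missingness. The first conclusion is a matter of principle and does not rest on the assumed rates.

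The size is conditional on a missing rate that the documents do not give. If staining answers are almost complete in both arms, the effect is negligible. At true success of 90–95%, reaching 1.3 to 6.7 points through under-recorded successes takes the heavy missingness shown in Step 2. The direction that can matter at low missingness is unrecorded failures, where 5% missing could shift one arm by up to about 5 points. That is an extreme case, not an expectation. These figures assume that the covariates do not predict success and that only one arm is affected. They are on the proportion scale, whereas the planned regression for binary outcomes is logistic.

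It would go too far to call the primary comparison unprotected. Imputation can address missingness explained by observed variables that are in its model. What is absent is any view of what happens when that explanation fails. The plan should be changed before analysis, but no bias has been shown.

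**What to change.** In Section 4:

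1. Delete the MCAR/MAR/MNAR classification. State MAR as the assumption of the main analysis, and include treatment arm and staining outcome in the imputation model.
2. Report, by arm and for each of the two product comparisons, the share of eyes with recorded staining answers. Count the separate ILM items in pucker surgery only where the ILM was removed separately, so that not-applicable is not read as missing.
3. Pre-specify a delta-adjusted (tipping-point) analysis of staining success, with the shift applied separately in the study and control arms over a stated range.
4. State the non-inferiority margin. Sections 2.3 and 4 give none, and without one the tipping point has no threshold. Say in advance over what part of the range the conclusion must hold.

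The cost is some SAP wording and one added analysis on the same data, plus agreement on a margin and a shift range, which takes clinical input. The conclusion may have to be stated less firmly.

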## STUDY SYNOPSIS

Title of clinical Study («Study»)	Efficacy and safety evaluation of MONOBLUE DUAL View and MONOBLUE ILM View vital stains during vitrectomy surgery
Protocol Short Title Acronym	NewBlueDyes
Sponsor name	University Hospitals Leuven (UZ Leuven)>
Principal Investigator	[name]. [name]
Contact Address PI	UZ Leuven, [name]
Contact Email PI	[contact]
Contact Phone PI	[name]
Other public database nbr	NA
Coordinating Investigator	NA
Medical devices	Monoblue Dual View Monoblue ILM View
Study rationale	Retrospective Data Collection
Primary objective	Efficacy: visualization of membranes stained based on binary subjective evaluation.
Secondary objective(s)	

• Efficacy: subjective assessment of surgical help provided by the product

• Safety:

○ Rate and severity of potential study-related products adverse events

○ Visual outcome at the last postoperative visit

Endpoints	Effectiveness Outcomes: Improvement in BCVA after 2 months as compared to preoperative BVCVA. Safety Outcomes: Safety will be assessed based on incidence and severity of investigational device-related adverse events.
Time frame of collecting data for retrospective analysis	SEPTEMBER 2021-APRIL 2022

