A few years later, Brilliant Blue G (BBG) was commercialized to selectively stain ILM, and is today still the golden standard for ILM staining. BBG offers a good and selective staining of the ILM, and is a rather transparent solution, hence the surgeon can see the surface of the retina during the surgery. However, BBG hardly stains the ERM.

The first commercial TB and BBG vital dyes were dissolved in BSS, hence had the same gravity as the BSS used to infuse the eye during vitrectomy surgery. As a result, when injecting a 'cloud' of the vital dye, it was difficult for the dye to reach and color specifically the desired retinal tissue. In newer commercial products, the dyes are dissolved in a heavier-than-water dissolvent (such as poly-ethylene glycol: PEG), which makes them sink down to the retinal surface when injected in the vitreous cavity during surgery.

Since it is frequently necessary to remove both ILM and ERM during vitrectomy surgery, solutions that combine TB and BBG are now also available.

In UZLeuven, two types of vital stains are being used during vitrectomy surgery:

- BBG 0,025 % dissolved in PEG (ILM Blue® – DORC): when only ILM peeling is required.
- BBG 0,025 % + TB 0.15% dissolved in PEG (Membrane Blue Dual® – DORC): when either ERM removal is required, or combination of ERM + ILM removal.

More recently, two new staining dyes were commercialized by ARCADOPHTA:

- Monoblue ILM View: DDG 0.025 % dissolved in PBS (phosphate buffer saline) with 2.6% diglycerol. DDG is a triphenylmethane dye with a chemical formula:  $C_{46}H_{46}N_3NaO_7S_2$  and a molecular weight of 840 Dalton. This dye is used to stain the ILM, similar as ILM Blue. The diglycerol makes it heavier than water to optimize the contact between the dye and the retina, similar as ILM Blue.
- Monoblue Dual View: DDG 0.025 % and Trypan Blue 0.09% dissolved in PBS with 2.6% diglycerol, which is used the same way as Membrane Blue Dual.

In laboratory and ex vivo tests, it was shown that both dyes have the following properties:

- Monoblue ILM view:
  - It stains ILM as good as ILM Blue.
  - It is heavier than water, hence sinks down to the retinal surface.

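### Indication (macular hole or vitreomacular traction) is left out of the adjustment and not named for the balance check in the non-randomised ILM dye comparison, so confounding of visual outcome cannot be excluded

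*Combined protocol and SAP*

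**What the plan says.** **Adjustment set.** Section 4 states: "The next covariates were selected for the propensity score: age, gender, visual acuity of the affected eye, surgery type of the affected eye". It defines surgery type as vitrectomy alone or combined with phaco. Section 2.3 gives the same four: "covariates (age, gender, visual acuity in the affected eye, surgery type being vitrectomy or phaco plus vitrectomy". The outcome regressions "will include the treatment group effect, the weight resulting from the matching, and variables present in the propensity score", so they add nothing to the list.

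**Balance.** An absolute standardised difference below 10–15% "will be considered to support the assumption of balance between the groups". The variables to be checked are not listed. The controls are described in section 4 only by the intention of "comparing the surgical outcome of the patients to a similar control group", with no criterion for indication.

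**Who is compared.** Section 3.1 lists macular hole and vitreomacular traction for ILM staining, and macular pucker for ILM plus ERM staining. The Background says that ILM Blue is used "when only ILM peeling is required". Section 4 fits one propensity score to the whole ILM dye pair, and section 5.2 puts macular hole and traction in one branch of the primary endpoint. Section 2.1 draws the controls from three earlier studies: two gauge comparisons and a field observation study.

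**Endpoint.** Section 5.2 lists as a safety endpoint "Visual outcome at the last postoperative visit, i.e. week 6-10 after the surgery". The synopsis gives as the effectiveness outcome "Improvement in BCVA after 2 months as compared to preoperative BVCVA".

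**The concern.** The disease being operated on is an obvious candidate predictor of vision after surgery, and nothing in the design makes its distribution equal in the two dye groups. The doubly robust estimator tolerates a wrong propensity model or a wrong outcome model. It does not help with a variable that both models omit. Because the balance variables are not listed, the plan can declare balance while indication is uneven, and it requires no table that would show this.

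Visual outcome in the ILM pair is what is at stake. Section 2.1 says the results may support a change of the hospital's standard dye, and section 4 describes the planned estimate as unbiased without stating the condition on which that depends.

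**Working it through.** The plan states no figure on this point, so there is none to reproduce. The check has a textual part and an illustrative part.

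**1. Text.** Could indication enter by another route?
- Surgery type encodes phaco, not indication.
- The exact match requested in section 4 is tied to the covariate balancing and does not mention indication.
- No section provides stratification, restriction, subgroup or sensitivity analysis by indication.

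**2. Formula.** When the four covariates are exactly balanced by the weights,

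bias = (difference in macular-hole share left after weighting) × (outcome gap between indications at equal covariates).

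**3. Inputs, all assumed.** No dye effect; 300,000 eyes per arm; average macular-hole share 50%; mix difference 10, 20 or 30 points. Baseline acuity has SD 0.3 logMAR within indication and a gap of 0, 0.2 or 0.4 between indications. Age, gender and phaco are unrelated to indication. Final acuity = 0.5 × baseline + (total gap − 0.5 × baseline gap) × macular hole + noise (SD 0.2). Weights are just-identified CBPS for the ATE, followed by weighted regression on group and the four covariates. One letter = 0.02 logMAR. The acuity covariate is taken as preoperative, which section 4 does not state.

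**4. Worked case.** Total gap 0.2, baseline gap 0.2: conditional gap = 0.2 − 0.5 × 0.2 = 0.1. Mix left after weighting is 8.9, 18.0 and 27.3 points, so the formula gives 0.0089, 0.0180 and 0.0273 logMAR. Simulated: 0.0088, 0.0186 and 0.0279.

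| Total gap | Baseline gap | Conditional gap | Bias at 10 / 20 / 30 points (logMAR) | Letters |
|---|---|---|---|---|
| 0.2 | 0 | 0.2 | 0.0202 / 0.0398 / 0.0596 | 1.0 / 2.0 / 3.0 |
| 0.2 | 0.2 | 0.1 | 0.0088 / 0.0186 / 0.0279 | 0.4 / 0.9 / 1.4 |
| 0.2 | 0.4 | 0 | 0.0005 / −0.0004 / 0.0002 | 0 |
| 0.1 | 0.2 | 0 | about 0 | 0 |
| 0.1 | 0.4 | −0.1 | −0.0059 / −0.0147 / −0.0212 | −0.3 / −0.7 / −1.1 |

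Repeat runs moved these by up to about 0.002 logMAR (0.1 letter). With indication in both models the bias was at most 0.0013 logMAR (under 0.1 letter). At an average share of 80% the letter figures for a total gap of 0.2 agree to within 0.1 letter.

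**5. Would a balance check show it?** Standardised difference in indication left after weighting, at 10 / 20 / 30 points:
- Share 50%: 18 / 37 / 57% (baseline gap 0.2); 14 / 28 / 43% (gap 0.4).
- Share 80%: 24 / 49 / 77% (gap 0.2); 20 / 41 / 66% (gap 0.4).

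Only the 14% case falls within the plan's 10–15% band. Even a raw split of 75% against 70% gives 0.05 / √[(0.75 × 0.25 + 0.70 × 0.30)/2] = 0.112. A table that included indication would therefore usually reveal the problem.

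**6. Precision cost.** Assumed 30, 50 or 100 eyes per arm, since no sample size is given; 20-point mix difference; baseline and total gap 0.2; 1,000 datasets per setting.

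| Eyes per arm | Traction share | Effective sample size, without → with indication | SD of estimate, without → with |
|---|---|---|---|
| 30 | 50% | 0.919 → 0.858 | 0.0559 → 0.0570 |
| 30 | 20% | 0.919 → 0.824 | 0.0577 → 0.0610 |
| 50 | 50% | 0.951 → 0.899 | 0.0421 → 0.0423 |
| 50 | 20% | 0.951 → 0.861 | 0.0407 → 0.0424 |
| 100 | 50% | 0.974 → 0.931 | 0.0288 → 0.0288 |
| 100 | 20% | 0.974 → 0.897 | 0.0303 → 0.0307 |

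The largest rise in SD is 0.0610/0.0577 = 1.06.

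**7. Rare traction.** At 5% against 15% traction, the chance that the 5% arm has no such eye is 0.95^30 = 0.21, 0.95^50 = 0.08 and 0.95^100 = 0.006. Simulated failure to balance was 21%, 7% and 0.6%.

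**The case against.** Confounding needs both a different mix and an effect of indication on vision at equal baseline acuity, and the documents show neither. An unlisted covariate can be named in almost any non-randomised comparison. Baseline acuity is already in both models and absorbs part of any effect; in two rows of the table it absorbs all of it. In the middle scenario the 20-point bias is also modest against sampling error: 0.0186/0.0559 = 0.33 SD at 30 eyes per arm and 0.0186/0.0288 = 0.65 SD at 100. Pooling of the two indications is inferred from the single propensity score and the shared endpoint branch; it is not stated in words.

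Much of this stands, and it limits the claim to something that cannot be excluded. It does not remove the point. Indication must be known to apply section 3.1, two of the plan's own groups are defined by it, and unknown size is a reason to report the mix.

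Three stronger readings are tempting, and the documents do not support them:
- **The non-inferiority conclusion is biased.** That hypothesis concerns staining success, and section 5.2 gives both indications the same questions and the same success rule. Nothing shows that success depends on indication.
- **The exclusion of concomitant eye disease (section 3.2) shows that indication affects outcome.** It concerns other disease in the eye, not the disease operated on.
- **The Dual View comparison has the same flaw.** Macular pucker is the only indication listed there for ILM plus ERM staining, so it is less exposed.

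**Conclusion.** The point holds for visual outcome in the Monoblue ILM View against ILM Blue comparison. Indication is absent from the propensity score and from the outcome regression, and is not named for the balance check. A difference in indication mix could therefore pass into the estimated dye effect unseen.

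Size and sign are unknown. In the assumed scenarios the bias is zero in some, about half a letter to 1.5 letters in the middle case, and 3 letters at most; that maximum needs a 30-point mix difference, a 0.2 logMAR outcome gap and no baseline gap. The sign can reverse. A reader might infer that the plan favours the new dye, or that adverse-event rates are distorted; the documents give no basis for either, and no figure is offered. This is an improvement that should be made to a secondary analysis, held with medium confidence. It is not a defect of the primary analysis.

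**What to change.** In the ILM comparison:
1. Record macular hole and vitreomacular traction separately in the eCRF, if they are not already separated.
2. Add indication to the propensity score and to the linear regression for visual outcome.
3. List the balance-check variables in section 4, include indication in the standardised-difference table, and report the mix per arm before and after weighting.
4. In the logistic models for staining success and adverse events, rely on the weights. Add an indication term only as a sensitivity analysis, if events allow, because its cost with few events has not been assessed.
5. If one indication is too rare in an arm to balance, report the imbalance and give visual outcome adjusted for indication or restricted to the commoner indication. Where an arm has no eyes with one indication, only the restricted analysis avoids extrapolation.
6. Where section 4 calls the effect unbiased, add that this requires no unmeasured confounding beyond the listed covariates.

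The cost is SAP wording, one covariate and possibly one eCRF field. With 30–100 eyes per arm and a 20-point mix difference, effective sample size falls from 92–97% to 82–93% of eyes and the SD rises by 0–6%. With no mix difference, effective sample size falls by at most about 2 points and the SD does not rise. These costs are for a continuous outcome only.
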